Radiofrequency (RF) Ablation Prospective Outcomes Study

**RAPID
Clinical Investigation Plan**

(A4087)

Sponsored By

Boston Scientific Neuromodulation Corporation
[name]
[name]
United States of America

This protocol contains confidential information for use by the Investigators and their designated representatives participating in this clinical investigation. The protocol should be held confidential and maintained in a secure location.

Do not copy or distribute without written permission from Boston Scientific Corporation.

[REDACTED]

[REDACTED]

Contact Information

| | |
|------------|------------|
| [REDACTED] | [REDACTED] |
| [REDACTED] | [REDACTED] |

Original Release: 09 OCT 2020

Current Version: 12 DEC 2023

[REDACTED]

[figure not shown]
2. Protocol Synopsis

| RAPID: RF Ablation Prospective Outcomes Study | |
|---|--|
| Study Objective | To compile real-world outcomes of Boston Scientific commercially approved radiofrequency (RF) ablation systems in the treatment of patients diagnosed with pain. |
| Indication(s) for Use | All commercially approved Boston Scientific radiofrequency ablation systems will be used as indicated per local directions for use. Refer to the applicable Directions for Use for detailed indication(s) for use. |
| Commercial Device/System | All commercially approved Boston Scientific RF Systems |
| Study Design | Prospective, multi-center, global outcomes study |
| | |
| | |
| Clinical Endpoints | 
The following endpoints will be evaluated. Assessments required for deriving each endpoint are denoted in parentheses.
 
 Proportion of subjects with a 30% or greater reduction from Baseline in targeted pain¹ intensity (VRS) at 1-, 3-, 6- and 12-months post-procedure Proportion of subjects with a 30% or greater reduction from Baseline in targeted pain¹ intensity (PPR) at 1-, 3-, 6- and 12-months post-procedure Change in targeted pain¹ intensity from Baseline Visit through 1-, 3-, 6- and 12-months post-procedure (VRS) Percent Pain Relief in targeted pain¹ through 1-, 3-, 6- and 12-months post-procedure (PPR) Patient global impression of change at 1-, 3-, 6- and 12-months post-procedure (PGI-C) |

[figure not shown]
| RAPID: RF Ablation Prospective Outcomes Study | |
|---|---|
| | 
 • Change in disability from Baseline Visit to 1-, 3-, 6- and 12-months post-procedure (ODIv2.1a) • Change in opioid pain medications from Baseline Visit to 1-, 3-, 6- and 12-months post-procedure (Concomitant Medications) 
¹Targeted pain – Pain intended to be treated using RF
 |
| Health Economic Endpoints | 
 • Economic value post-procedure (RUI, EQ-5D-5L, Concomitant Medications, Procedure Information) |
| Safety Parameters | 
 • Rate of occurrence of all device-related and procedure-related non-serious adverse events (AEs) • Rate of occurrence of all serious adverse events (SAEs) and unanticipated adverse events |
| Follow-up Schedule | 
 • Baseline Visit • Procedure Visit (Day 0) • 1-Month Post-Procedure Visit (30 + 14 days) • 3-Month Post-Procedure Visit (90 ± 14 days) • 6-Month Post-Procedure Visit (180 ± 30 days) • 12-Month Post-Procedure Visit (365 ± 30 days) • Additional RF Procedure for any additional RF procedure(s) • Unscheduled visits as needed for the study and as required for additional RF procedure(s) |
| | |
| | |
| Key Inclusion Criteria | 
IC1. Study candidate is scheduled to be treated with a commercially approved Boston Scientific RF system for pain per local Directions for Use (DFU)
 
IC2. Signed a valid, IRB/EC/REB-approved informed consent form
 |

| RAPID: RF Ablation Prospective Outcomes Study | |
|---|--|
| | |
| Key Exclusion Criteria | 
EC1. Meets any contraindications per locally applicable Directions for Use (DFU)
 
EC2. Currently diagnosed with cognitive impairment, or exhibits any characteristic, that would limit study candidate's ability to assess pain relief or to complete study assessments
 |
| Statistical Methods | |
| Primary Statistical Hypothesis | Descriptive statistics will be utilized to report the clinical endpoints and their changes from baseline at 1-, 3-, 6- and 12-months post-procedure. |

Study Schematic

[REDACTED]

[REDACTED]

[REDACTED]

4. Introduction

4.1. *Chronic Intractable Pain*

Chronic intractable pain is often defined as pain persisting for at least 6 months which has not responded to conservative treatment(s). The pain may be due to current or past nerve injury and causes significant disability, reduced work productivity, reduced quality of life, and significant cost burden.

The complexity of chronic pain and the diverse population it affects have resulted in varying results between the various treatment approaches including medications, physical therapy, stimulation etc. Early treatments for chronic pain typically include over the counter and prescription medications. Later treatment typically includes physical therapy before any interventional pain procedures, such as radiofrequency ablation (RF), are attempted.

4.2. *Thermal Radiofrequency Ablation*

Radiofrequency (RF) ablation is a minimally invasive procedure that uses heat to reduce or stop the transmission of neurological signals. During the procedure, an insulated needle is used to create a small lesion within a nerve to disrupt the neurological signal. The needle has high-frequency electrical current passing through it, which creates an electric field at the tip of the needle. The electric field produces thermal energy via molecular movement, resulting in enough heat produced at the needle tip to apply the lesion (Shealy, 1975).

Radiofrequency ablation (RFA) was first introduced in 1931 with the treatment of trigeminal neuralgia (Krischner, 1931). In the mid-1950's, RF was used in thalamotomy procedures in the brain (Alajouanine & Houdart, 1957) and has since expanded into a multitude of useful applications. These include treatment of chronic low back pain, sciatica, and rhizotomy of problematic nerve roots in the spinal cord in the 1970's (Uematsu, Udrarhelyi, Benson, & Seibens, 1974; Shealy, 1975), and catheter ablation of the heart in the 1980's (Scheinman, Morady, Hess, & Gonzalez, 1982).

RF ablation has been shown to be effective for chronic intractable pain originating from a variety of locations, including, but not limited to cervical zygapophyseal (Lord et al., 1996), lumbar zygapophysial (van Kleef et al., 1999), sacroiliac (Cohen et al., 2008), hip (articular branches of the femoral and obturator nerves), and knee (genicular nerve) (Choi et al., 2011) joints.

While there are randomized controlled studies evaluating RF for chronic pain that reported negative or equivocally positive results, most have shown improvement in outcomes for patients with chronic pain treated with RF compared to baseline, although some control groups also improved correspondingly (Chen, et al., 2015; Cho, Cho, Kwak, & Chang, 2017; Cohen, et al., 2015; Juch, et al., 2017; Luo, et al., 2017; Makharita & Amr, 2015; Pi, Lin, He, Cai, & Xu, 2015; Saxena AK, 2016; Van Tilburg, Stronks, Groeneweg, & Huygen, 2016; Wu YT, 2017) (Walega, McCormick, Manning, & Avram, 2019; Davis, et al., 2018; Mehta,

Poply, Husband, Anwar, & Langford, 2018; Fischgrund, et al., 2019; Hunter, Davis, Loudermilk, Kapural, & DePalma, 2019; McCormick, et al., 2019)

The largest controlled study to report negative results was Juch, et al., which evaluated the effectiveness of adding RF denervation to a standardized exercise program to treat chronic low back pain in multicenter, nonblinded, randomized trials (Mint study). Participants were eligible if they had chronic low back pain, a positive diagnostic block at the facet joints (facet joint trial, 251 participants), sacroiliac joints (sacroiliac joint trial, 228 participants), or a combination of facet joints, sacroiliac joints, or intervertebral disks (combination trial, 202 participants), and did not benefit from conservative care. All participants underwent a 3 month exercise program with the intervention group also receiving up to 3 RF denervation procedures. The primary outcome was NRS score at a follow up time of 3 months, with a minimal clinically important difference specified as 2 NRS points or more. Final follow-up was at 12 months. Among 681 randomized participants (mean baseline pain intensity=7.1), 599 (88%) completed the 3-month follow-up and 521 (77%) completed the 12-month follow-up. At 3 months, the mean difference in pain intensity between the intervention and control groups was -0.18 (95%CI, -0.76 to 0.40) in the facet joint trial; -0.71 (95%CI, -1.35 to -0.06) in the sacroiliac joint trial; and -0.99 (95%CI, -1.73 to -0.25) in the combination trial. The authors concluded that RF denervation near the facet joint, sacroiliac joint, or intervertebral disk was no different than a standardized exercise program for treating chronic low back pain (Juch, et al., 2017). These conclusions are untenable for numerous reasons; significant methodological flaws exist in the study including design and analysis, patient selection and inclusion/exclusion criteria, outcome measurement, and diagnostic block and RF techniques to name a few (Provezano, Buvanendran, de Leon-Casasola, Narouze, & Cohen, 2018; McCormick, et al., 2018; Vorobeychik, Stojanovic, & McCormick, 2017). Meaningful conclusions are difficult to draw from this study given the many flaws and drawing conclusions such as the authors did may prevent appropriately selected patients from receiving RF treatment performed with appropriate technique.

RF ablation performed with proper technique is an effective option in well-selected patients with chronic pain.

4.3. Study Rationale

The purpose of this outcomes study is to gather evidence of Boston Scientific commercially approved radiofrequency (RF) ablation systems in the treatment of patients diagnosed with pain.

5. (Commercial) Device Description (Part of Standard of Care)

This outcomes study includes all commercially approved Boston Scientific radiofrequency ablation systems, per local Directions for Use. Refer to the Directions for Use for detailed device description.

6. Study Objectives and Endpoints

6.1. Primary Objective

To compile real-world outcomes of Boston Scientific commercially approved radiofrequency (RF) ablation systems in the treatment of patients diagnosed with pain.

6.2. Secondary Objective

To evaluate the economic value and technical performance of Boston Scientific commercially approved radiofrequency systems for pain in routine clinical practice, when used according to the applicable Directions for Use.

6.3. Clinical Endpoints

The following endpoints will be evaluated. Assessments required for deriving each endpoint are denoted in parentheses.

- Proportion of subjects with a 30% or greater reduction from Baseline in targeted pain¹ intensity (*VRS*) at 1-, 3-, 6- and 12-months post-procedure
- Proportion of subjects with a 30% or greater reduction from Baseline in targeted pain¹ intensity (*PPR*) at 1-, 3-, 6- and 12-months post-procedure
- Change in targeted pain¹ intensity from Baseline Visit through 1-, 3-, 6- and 12-months post-procedure (*VRS*)
- Percent Pain Relief in targeted pain¹ through 1-, 3-, 6- and 12-months post-procedure (*PPR*)
- Patient global impression of change at 1-, 3-, 6- and 12-months post-procedure (*PGI-C*)
- Change in disability from Baseline Visit to 1-, 3-, 6- and 12-months post-procedure (*ODIv2.1a*)
- Change in opioid pain medications from Baseline Visit to 1-, 3-, 6- and 12-months post-procedure (Concomitant Medications)

¹Targeted pain – Pain intended to be treated using RF

Additional endpoints will be evaluated post-hoc for data collected in assessments not listed in the predefined clinical endpoints.

6.4. Health Economics Endpoints

The following health economics endpoints will be evaluated. Assessments required for deriving each endpoint are denoted in parentheses.

- Economic value at 1-, 3-, 6- and 12-months post-procedure (*RUI, EQ-5D-5L, Concomitant Medications, Procedure Information*)

6.5. Safety Parameters

The following safety endpoints will be evaluated.

- Rate of occurrence of all device-related and procedure-related non-serious adverse events (AEs)
- Rate of occurrence of all serious adverse events (SAEs) and unanticipated adverse events

[figure not shown]
7. Study Design

The study is a prospective, multi-center, global outcomes study of BSC radiofrequency ablation systems for pain. All participants will follow the study schedule as shown in study schematic Figure 7.1-1.

7.1. Scale and Duration

Figure 7.1-1: RAPID Design Schematic

7.2. Treatment Assignment

Consecutive eligible patients receiving radiofrequency ablation with the Boston Scientific RF system per standard of care who provide written informed consent to participation and have met all of the inclusion and none of the exclusion criteria will be enrolled in the study and assigned a unique subject identifier in the Electronic Data Capture (EDC) system.

8. Subject Selection

8.1. Study Population and Eligibility

Subjects are established patients in a medical practice (e.g. pain management, neurologist, surgical, physical medicine and rehabilitation) who will receive radiofrequency ablation therapy to treat pain utilizing a commercially approved BSC radiofrequency ablation system per local DFU according to standard of care.

8.2. Inclusion Criteria

Subjects who meet all of the following criteria (see Table 8.2-1) may be given consideration for inclusion in this clinical investigation, provided no exclusion criterion (see Table 8.3-1) is met.

Table 8.2-1: Inclusion Criteria

| | |
|-----------------------------|---|
| Clinical Inclusion Criteria | 
IC1. Study candidate is scheduled to be treated with a commercially approved Boston Scientific RF system for pain per local Directions for Use (DFU)
 
IC2. Signed a valid, IRB/EC/REB-approved informed consent form
 |
|-----------------------------|---|

8.3. Exclusion Criteria

Subjects who meet any one of the following criteria (Table 8.3-1) cannot be included in this study or will be excluded from this clinical study.

Table 8.3-1: Exclusion Criteria

| | |
|-----------------------------|--|
| Clinical Exclusion Criteria | 
EC1. Meets any contraindications per locally applicable Directions for Use (DFU)
 
EC2. Currently diagnosed with cognitive impairment, or exhibits any characteristic, that would limit study candidate's ability to assess pain relief or to complete study assessments
 |
|-----------------------------|--|

9. Subject Accountability

9.1. Point of Enrollment

A subject will be considered enrolled in the study when the Informed Consent Form (ICF) is signed. All treated subjects will be included in the intent to treat analyses and all treated subjects with no major protocol deviations will be included in the study analyses.

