11.1.1.3. Statistical Methods

No formal statistical hypothesis is planned. Descriptive statistics will be utilized to report the clinical endpoints and their changes from Baseline at 1-, 3-, 6- and 12-months post-procedure.

[REDACTED]
[REDACTED]
[REDACTED]
[REDACTED] who receive treatment with the study device, with no major protocol deviations.

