12.2. Study Assessments

12.2.1. Adverse Events

Adverse event evaluation will be conducted to identify adverse events occurring during the study and classify them in regard to seriousness, relationship to the procedure and/or device, action taken and outcome. Safety events will be reported as specified in Table 17.4-1.

All device and procedure related non-serious adverse events, all serious adverse events regardless of relatedness, and unanticipated adverse events will be collected from the time of consent through the end of the study.

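### Section 9.1 assigns the study analyses to treated subjects without major protocol deviations and does not make the all-treated set the main one

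*Combined protocol and SAP*

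**What the plan says.** Section 9.1 places enrolment at consent: "A subject will be considered enrolled in the study when the Informed Consent Form (ICF) is signed". It then defines two sets in one sentence. The first half reads "All treated subjects will be included in the intent to treat analyses"; the second half reads "all treated subjects with no major protocol deviations will be included in the study analyses".

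Section 11 has one visible fragment about an analysis set. It stands under 11.1.1.3 after redacted lines: "who receive treatment with the study device, with no major protocol deviations". The name and role of that set cannot be read. Section 11.1 lists the clinical endpoints and promises estimates with 95% confidence intervals, but names no set. Section 11.1.1 states that there is no primary endpoint, no sample size calculation and no formal hypothesis. Section 11.2.4 refers to a separate Statistical Analysis Plan for further detail.

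The primary objective in 6.1 is "To compile real-world outcomes of Boston Scientific commercially approved radiofrequency (RF) ablation systems in the treatment of patients diagnosed with pain", and section 7.2 enrols consecutive eligible patients.

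On safety, section 6.5 asks for, among others, the "Rate of occurrence of all serious adverse events (SAEs) and unanticipated adverse events". Section 12.2.1 sets the collection period for reportable events, ending with "unanticipated adverse events will be collected from the time of consent through the end of the study". Neither section names an analysis set or mentions a deviation filter.

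Section 13 requires every deviation to be recorded with its reason and date, and has the sponsor review deviations as the study proceeds. The visible text does not say what makes a deviation major, or when and by whom that is decided.

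**The concern.** Read plainly, *the study analyses* are the study's own results, and section 9.1 gives them to a subset chosen by deviation status. Some deviations, such as consent or eligibility errors, precede the procedure. Others can arise during or after it, and then membership of the set can depend on events that are themselves related to outcome.

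The product of this study is a set of descriptive rates, so the denominator is a central analytic decision. A study meant to show what happens to consecutive patients in routine practice should describe everyone treated. A subset selected in part after treatment answers a different question, and its rates may differ from those of the treated population. The visible text describes no comparison group and no blinding, and it does not rule out that deviations are classified by people who have seen the outcomes.

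**Working it through.** The documents give no number of subjects, no expected rates and no expected share with major deviations. There is no planned figure to reproduce. The check is a reading of the text, followed by an illustration on assumed inputs.

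**Step 1: what each section fixes.**

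| Question | Visible answer | Where |
|---|---|---|
| Is an all-treated analysis planned? | Yes, labelled intent to treat | 9.1 |
| Which set carries the *study analyses*? | Treated, no major deviations | 9.1 |
| Which set is the main one for the clinical endpoints? | Not stated | 11.1, 11.1.1.3 |
| What is a major deviation, and when is it classified? | Not stated | 9.1, 13 |
| Which set carries the safety rates? | Not stated | 6.5, 12.2.1 |

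**Step 2: formula.** Let d be the share of treated subjects excluded, p_k the responder rate in kept subjects and p_e the rate in excluded subjects.

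All-treated rate = (1 − d) × p_k + d × p_e

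Filtered rate minus all-treated rate = p_k − [(1 − d) × p_k + d × p_e] = d × (p_k − p_e)

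**Step 3: responder rates.** Assumed: p_k = 60%; p_e = 60%, 40% or 20% (gaps of 0, 20 and 40 points); d = 5%, 10% or 20%. The entries are the overstatement of the all-treated rate, in percentage points.

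| Excluded | Gap 0 | Gap 20 | Gap 40 |
|---|---|---|---|
| 5% | 0 | 0.05 × 20 = 1 | 0.05 × 40 = 2 |
| 10% | 0 | 0.10 × 20 = 2 | 0.10 × 40 = 4 |
| 20% | 0 | 0.20 × 20 = 4 | 0.20 × 40 = 8 |

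For example, with 20% excluded and p_e = 20%, the all-treated rate is 0.80 × 60% + 0.20 × 20% = 52%, against 60% in the filtered set. If excluded subjects did better than kept subjects, the sign would reverse.

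**Step 4: safety, only if the filter were applied there.** Assumed: an event rate of 3% in kept subjects and 3%, 6% or 15% in excluded subjects. With 20% excluded, the all-treated rate is 0.80 × 3% + 0.20 × 3% = 3.0%, 0.80 × 3% + 0.20 × 6% = 3.6%, or 0.80 × 3% + 0.20 × 15% = 5.4%. The filtered rate would be too low by 0, 0.6 or 2.4 points. With 5% excluded the shortfall would be 0, 0.15 or 0.6 points.

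**The case against.** The strongest reply is that section 9.1 already plans an all-treated analysis, that the study is descriptive with no confirmatory claim at stake, and that the rest of the analysis-set text is redacted or sits in a separate plan. The 11.1.1.3 fragment may simply define a per-protocol set beside an intent-to-treat set. Much of this stands. A reader might infer from section 9.1 that only a filtered subset will be reported; the first half of the same sentence rules that out. Nor can the redacted text be counted as missing.

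A reader might also infer that the safety rates fall under the filter because no other rule is visible. That is an argument from silence. Sections 6.5 and 12.2.1 point the other way: 6.5 asks for the rates of all such events, and 12.2.1 collects them without regard to deviations. What remains is that collecting events does not define the denominator of a rate.

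Two further inferences go too far. Deviation status is not always settled after treatment. And the two windows given for the 12-month visit (±30 days in the synopsis, ±60 in section 10.7) change the set only if a missed window counts as a major deviation, which the documents do not say.

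The redaction does not remove the core point. Section 9.1 is readable, current text. If the hidden text or the separate plan makes the all-treated set the main one, section 9.1 still needs to be brought into line with it.

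**Conclusion.** The point holds in a limited form. Both sets are planned, but section 9.1 attaches the study analyses to the deviation-free one, and no visible text makes the all-treated set the main set. Followed as written, this can put the descriptive rates on a selected denominator, contrary to the real-world objective.

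The size and direction of any bias are unknown. The 0 to 8 points for responder rates rests on assumed exclusion shares of 5% to 20% and assumed gaps of 0 to 40 points. It is zero if excluded and kept subjects respond alike. That exclusions remove poorer outcomes is plausible but not shown by the documents. For safety, the supported conclusion is only that the visible text names no set.

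**What to change.** Reword section 9.1 and align the analysis-set text in section 11 along these lines:

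*All treated subjects form the main analysis set for the clinical endpoints and the set for the safety rates. The set without major protocol deviations is used for a supportive sensitivity analysis of the clinical endpoints. Major deviations are defined in advance and classified before outcomes are reviewed.*

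The health-economic set can be specified separately, because the secondary objective in section 6.2 is tied to use within the Directions for Use.

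The cost is a few sentences in a protocol amendment, with the ethics review that section 14.3 requires, and matching text in the Statistical Analysis Plan. No new data are needed. The headline rate may be slightly less favourable, and the deviation-free tables become secondary.

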9.2. Withdrawal

All subjects enrolled in the clinical study (including those withdrawn from the clinical study) shall be accounted for and documented. If a subject withdraws from the clinical investigation, the reason(s) shall be reported. If such withdrawal is due to problems related to device safety or performance, the investigator shall ask for the subject's permission to follow his/her status/condition outside of the clinical study.

While study withdrawal is discouraged, subjects may withdraw from the study at any time, with or without reason and without prejudice to further treatment. In all cases of withdrawal or discontinuation, the Investigator will make all reasonable efforts to determine the reason for the subject's withdrawal. Subjects may be discontinued from the study for the various reasons, such as:

- Withdrawal of consent
- A safety concern defined by the Principal Investigator and/or Boston Scientific Neuromodulation (e.g., adverse event)

- Study non-compliance
- Inadequate use of device that may impact study outcomes
- Subject did not meet inclusion criteria or met an exclusion criterion after signing informed consent
- Subjects who decline an additional RFA procedure recommended by the study physician
- Lost to follow-up
- Death of the subject

A subject is considered lost-to-follow-up after a minimum of 3 unsuccessful contact attempts have been made to reach the subject (including those who relocate but cannot be transferred to another participating site). Staff at the participating site should make a good faith effort to contact the subject with three documented communication attempts, at least one of which must be in writing, sent via a traceable method.

Data collected up to the point of subject withdrawal or lost to follow-up may be used for study analysis in accordance with applicable regulations.

Withdrawn subjects will be followed per standard of care

